## TRIAL SUMMARY

[figure not shown]
Trial Title	Evaluation of Personalised Prehabilitation in people with acute myeloid Leukaemia (AML)
Short title	PROPEL
Clinical Phase	Phase III
Trial Design	Multicentre, randomised controlled trial comparing best practice usual care (BPUC) with a personalised prehabilitation care package (PPCP) incorporating a 12-month internal pilot, parallel process evaluation and economic evaluation.
Research Question	What is the clinical impact and cost-effectiveness of BPUC compared to PPCP on fatigue, emotional wellbeing, and quality of life (QoL) in patients receiving remission consolidation treatment for AML or high-risk myelodysplastic syndromes with excess blasts (MDS-EB2)?
Hypothesis	PPCP will improve patients' experience of fatigue during treatment in comparison to BPUC, through supporting patients to manage their emotions, be physically active, and eat an appropriate diet.
Trial Participants	Diagnosis of AML or MDS-EB2, in complete remission following induction chemotherapy.
Inclusion Criteria	
Aged <math>\geq 16</math> years with either:
 
 
• Diagnosis of AML or MDS-EB2 (MDS with <math>\geq 10\%</math> blasts in the bone marrow),
 
• In complete remission at completion of induction chemotherapy (defined <math>< 5\%</math> blasts in bone marrow), with an intention to undertake full consolidation treatment (chemotherapy +/- Haemopoietic Stem Cell Transplant (HSCT)), aimed at cure.
 
 
or
 
 
• Relapsed AML who have achieved a further complete remission with an intent to deliver further intensive consolidation treatment +/- HSCT.
 

Exclusion Criteria	
 
• People with Acute Promyelocytic Leukaemia
 
• Undergoing non-intensive treatment (e.g., single agent Azacitidine, low dose Cytarabine).
 

Planned sample size	600 patients; 300 per arm.

Treatment Duration	Treatment duration will vary according to number of cycles of chemotherapy and whether a HSCT is given. Each cycle of treatment and recovery is 4-6 weeks duration.
Follow-up Duration	Primary and secondary outcomes will be assessed at the first 3 months follow up post completion of treatment (either chemotherapy or HSCT) and at 24 months post randomisation. Annually up to 60 months for relapse free survival and overall survival.

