Primary	To compare subjective levels of fatigue between patients in BPUC and PPCP arms	Functional Assessment of Chronic Illness Therapy (FACIT-F) fatigue scale
Secondary	To compare the following between participants in BPUC and PPCP arms:	
	Emotional wellbeing	Warwick-Edinburgh Mental Wellbeing Scale (WEMWBS)
	Anxiety and Depression	Patient Health Questionnaire 9-item (PHQ-9)  General Anxiety Disorder 7-item (GAD7)
	Health Related Quality of Life	FACIT-F  EQ-5D-5L
	Physical function	Karnofsky Performance Scale  6 min walk test  Hand grip strength
	Presence or absence of sarcopenia	SARC-F  Calf circumference
	Incidence of malnutrition and its determinants	MUST, Percentage weight change; BMI, dietary intake (food diary)

	Completion of treatment cycles	Number of cycles of chemotherapy completed +/- HSCT.
	Onward referrals for 'specialist' services	Number of onward referrals to local services for 'specialist' therapies
	Overall and relapse-free survival	Relapse, Death
	Readmissions to hospital, ICU admission, number of transfusions, complications of HSCT, adverse events and serious adverse events	Number of hospital admissions, transfusion, and complications of HSCT
	Cost, cost-effectiveness and cost utility	Resource use costs Cost EQ-5D-5L
	Parallel process evaluation: to understand the implementation and functioning of the intervention in context	Evaluation through qualitative interviews.  Intervention delivery fidelity assessment of a proportion of sessions; patient intervention dose assessment through trial designed measurement tools
	Mechanisms of Action: Psychological Flexibility (PF), Motivation	CompACT-8  COM-B Questionnaire 1-item Motivation

Figure 1: Trial Schema

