# 1 BACKGROUND

## 1.1 Epidemiology and treatment of AML

AML is the most common acute leukaemia affecting all ages in adults (2500 people/year in UK), often presenting as a medical emergency. Intensive chemotherapy forms the backbone of treatment in the NHS aiming at cure (over 1300 people/year), with an overall survival of 20% at 5 years in adults [1]. In 2019, across the UK, just over 600 patients were transplanted for AML and a related disease high-risk myelodysplastic syndrome (MDS with excess blasts; MDS-EB2), which is treated along the same pathway as AML. Completion of all cycles of treatment is important prognostically [1].

The first cycle of chemotherapy (induction) usually starts within days of diagnosis with little opportunity for conventional timing of prehabilitation, a point reiterated by our PPI panel. This first cycle is followed by an additional 2-3 cycles of consolidation chemotherapy, with ~40% requiring HSCT [curative intent & indicated by risk of relapse [2]]. Each cycle is 4-6 weeks, separated by 1-2 weeks for full blood cell regeneration. Overall treatment is either at home or in hospital and can be for a total of 6 months. Being able to tolerate HSCT is an important consideration when discussing treatment and cure options with patients.

PROPEL is addressing the challenge of how to reduce fatigue, increase emotional wellbeing and quality of life (QoL), enabling people with AML to prepare for and complete all intensive chemotherapy treatments.

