### 2.2.2 Secondary Outcomes:

- Emotional wellbeing: the Warwick-Edinburgh Mental Wellbeing Scale (WEMWBS) assesses participant's mental wellbeing and consists of 14 items, scored on a 5-point Likert scale score, giving an overall score [12].
- Anxiety and Depression: Patient Health Questionnaire 9-item (PHQ9) measures severity of depression and response to treatment. General Anxiety Disorder 7-item (GAD7) assesses the likelihood of the presence of the four most common clinical anxiety disorders [13, 14].
- Health-related quality of life:
  - FACIT F incorporates the 27 item FACT-G (Functional Assessment of Cancer Therapy – General) and measures four domains of health-related quality of life: physical, social, emotional and functional well-being.
  - EQ-5D-5L measures health status in 5 dimensions plus a visual analogue scale of self-rated health status [15].
- Physical function:
  - Performance Status: the Karnofsky Performance Scale Index allows patients to be classified as to their functional impairment, used in (p)rehabilitation [16].
  - The 6-minute walk test [17].
  - Hand grip strength [18].
- Incidence of sarcopenia: SARC-F [19]; calf circumference [20].
- Incidence of malnutrition: Utilising Malnutrition Universal Screening Tool (MUST) [21] and its determinants; % weight change, Body Mass Index (BMI), energy and protein intake (food diaries via myfood24) [22].
- Completion of consolidation treatment plan (chemotherapy +/- HSCT)
- Number of onward referrals to local services for 'specialist' therapies.
- Overall and relapse-free survival.
- Readmissions to hospital, ICU admission, number of transfusions, complications of HSCT, adverse events and serious adverse events.
- Costs, cost-effectiveness and utility: costs, health resource use and EQ-5D-5L.
- Process Evaluation: fidelity to intervention delivery and dose of intervention received for each component.
- Mechanisms of Action:
  - Psychological flexibility – is the mechanism of action for ACT, and the model within which all intervention methods are delivered. This will be measured with a shortened version (8-items) of the CompACT questionnaires [23]
  - Motivation – measured using 1-item from the COMB-Q adapted for each component (3-items total) [24].

All questionnaires being used for the patient reported outcomes have been previously validated or have been adapted from validated questionnaires to fit this specific context and patient group.

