## **8 STATISTICAL ANALYSIS**

### **8.1 Power and sample size**

A sample size of 300 patients in each arm (600 in total) will allow the detection of a standardised difference of 0.3 in the continuous fatigue subscale scores of the Functional Assessment of Chronic Illness Therapy fatigue scale (FACIT-F) for the comparison of PPCP and BPUC with 90% power, 5% two-sided significance and allowing for 20% dropouts. The sample size calculation was determined using the POWER procedure within the SAS statistical software for a two-sample t-test.

A standardised difference of 0.3 equates to a minimally important clinical difference (MCID) of 4 points with a standard deviation of 13 using the FACIT-F fatigue subscale (which is a 13 item scale with scores 0-52) [11]. This MCID was based on the previous research from other studies [1] and considered acceptable after discussions with fatigue experts, AML clinicians and our PPI representatives.

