### **8.2 Statistical analysis of efficacy and harms**

#### **8.2.1 Statistics and data analysis**

A detailed statistical analysis plan (SAP) will be produced to provide full details of all statistical aspects of the study. All analyses and reporting of outcomes will be in accordance with CONSORT [52], with primary analysis conducted according to randomised allocation and intention to treat principles.

The primary analysis will be a pragmatic comparison of the PPCP versus BPUC on an intention to treat basis to preserve randomisation and avoid bias. Sensitivity analyses will investigate the effect of the personalised nature of the intervention on any treatment effects and the effect of compliance using a complier averaged causal effect (CACE) analysis.

All measures will be scored according to the appropriate scoring manual and summary measures obtained for each timepoint. A longitudinal mixed effects regression model will be used to estimate the effect of the intervention compared to standard care on fatigue adjusted for patient-level factors including age, performance status and treatment received. The specialist that delivers the interventions will also be considered for inclusion as a random effect in the model although we expect the variation to be negligible due to the large number of specialists across sites. The effect of red cell transfusion use on the outcome will be considered as time-dependent effect, considering haemoglobin levels and timing of transfusions, as anaemia is a universal complication in AML. The individual need, compliance and intensity of the intervention including the number and amount of each component delivered will be investigated and their need for inclusion in the mixed effects regression model evaluated. Exploratory analyses will investigate intervention and covariate interactions to identify any subgroups where the intervention may work differently to the whole population.

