Similar longitudinal analyses will be performed for the secondary QoL outcomes. Time to event outcomes, including the overall survival and relapse-free survival, will be assessed using Kaplan-Meier curves and compared across trial arms using Cox proportional hazards models, adjusted for the stratification factors. The impact of fatigue on these time to event outcomes will also be evaluated using Cox models. Completion of consolidation treatment plan including chemotherapy and HSCT, readmissions to hospital, ICU admission, number of transfusions, complications of HSCT will be compared across trial arms using logistic regression models. Adverse events and serious adverse events will be tabulated and compared if appropriate.

A sensitivity analysis will be considered to determine the degree to which the conclusions may change with different missing data assumptions and mechanism models.

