## **8.3 Health Economics Evaluation**

The within trial analysis will be from the perspective of the NHS and personal social services (PSS) and will determine the cost-effectiveness and the cost-utility of a personalised prehabilitation (PPCP) compared to best practice usual care (BPUC). The primary effectiveness measure for the cost-effectiveness analysis will be change in FACIT-F and for the cost-utility analysis will be quality-adjusted life year (QALY). To estimate QALYs, health-related quality of life will be measured at baseline, post each chemotherapy cycle and three-months after completion of final cycle using the EQ-5D-5L measure. Using the trapezoidal rule, responses to the EQ-5D-5L will be converted into health utilities using the most appropriate utility algorithm as recommended by NICE [15]. The resource use questionnaire booklet will collect information on prehabilitation usage (including staff training, follow-up phone calls, weekly check-ins etc), specialist referrals, hospital admissions including readmissions and ICU admissions, number of transfusions, GP visits, complications of HSCT, and adverse events. This booklet will be first administered prior to cycle 2, and will collect the resource use data from baseline up until EOT. Unit costs will be estimated from local and national reference costs and reflatd to current prices and will be applied to each resource item to value total resource use in each arm of the trial. These costs and outcomes will be aligned with the NICE-reference case using bivariate regression of costs and outcomes which will inform a probabilistic assessment of incremental cost-effectiveness including 95% confidence intervals around mean cost and QALY differences between the trial groups. The incremental cost-effectiveness ratios (ICERs) will be expressed as cost per improvement in FACIT-F and cost per QALY gained. Results will be shown on a cost-effectiveness plane and plotted as cost-effectiveness acceptability curves. Sensitivity analyses will be undertaken to explore cost-effectiveness uncertainty and generalisability. As part of the sensitivity analyses, using a societal perspective we will look at the broader implications of costs and benefits associated with the personalised plan to patients and their families.

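### Section 8.2.1 assigns the number of transfusions, and readmissions that the Trial Summary measures as a number, to logistic regression with no coding stated

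*Protocol*

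**What the plan says.** Section 8.2.1 places four outcomes alongside completion of the treatment plan and gives them all one model: "readmissions to hospital, ICU admission, number of transfusions, complications of HSCT will be compared across trial arms using logistic regression models".

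The type of outcome is described in three ways:

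- The Trial Summary gives the measure as "Number of hospital admissions, transfusion, and complications of HSCT".
- Section 2.2.2 lists "Readmissions to hospital, ICU admission, number of transfusions, complications of HSCT, adverse events and serious adverse events". Here transfusions are a number, while readmissions are not called one.
- Section 8.3 includes the number of transfusions, and hospital admissions including readmissions, in the resource use booklet.

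On observation time, the Trial Summary says "Treatment duration will vary according to number of cycles of chemotherapy and whether a HSCT is given", and section 1.1 describes an "additional 2-3 cycles of consolidation chemotherapy, with ~40% requiring HSCT". Section 8.3 says the booklet "will collect the resource use data from baseline up until EOT", whereas the schedule in section 4.9 also shows the health resource use questionnaire at 3 months after end of treatment (EOT) and at month 24.

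Section 8.2.1 states no cut-point, coding, ordinal form or time at risk for these outcomes. The only hint of how common transfusion is comes in its paragraph on the fatigue model, which says that "anaemia is a universal complication in AML". No transfusion or admission frequency is given anywhere.

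**The concern.** A count cannot enter a binary logistic model until someone chooses how to split it. The protocol names the model but not the split, so a statistical analysis plan that follows section 8.2.1 must supply one. If it is supplied late, it can be chosen with the data in view.

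Two things are at stake. The first is information: if nearly every patient is transfused and the split is any versus none, almost all patients fall in one category. The second is exposure. Patients who receive more cycles, or a transplant, are observed on treatment for longer and have more opportunity for admission and transfusion. Completing treatment is itself an outcome that the intervention aims to improve, so time on treatment may differ by arm.

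**Working it through.** **The protocol's own figure.** Section 8.1 powers the trial for a "standardised difference of 0.3 in the continuous fatigue subscale scores" with 90% power at two-sided 5%. By the normal approximation, n = 2(1.960 + 1.282)² / 0.3² = 234 per arm (235 by exact t). Dividing by 0.8 for 20% dropout gives 293 (294), against 300 stated. This reproduces. The evaluable number used below is 300 × 0.8 = 240 per arm.

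**Assumptions, since the protocol gives no rates.** Rate ratio 0.8; mean count μ of 10 to 20 for transfusions and 1 to 2 for readmissions, with 5 in between; negative binomial dispersion k of 0.3, 0.5 and 1.0; equal follow-up in this part.

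**Formulas.**

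- Proportion with at least one event: p = 1 − (1 + kμ)^(−1/k).
- Logistic, any versus none: power = Φ(|log OR|/SE − 1.96), with SE² = Σ 1/[n p(1 − p)] over the two arms. The median split uses the same formula, with p the proportion above the control median.
- Negative binomial: power = Φ(|log 0.8|/SE − 1.96), with SE² = Σ (1/μ + k)/n over the two arms.

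**Worked case: mean 10 versus 8, k = 0.5.**

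- Any event: 1 − 6⁻² = 0.972 and 1 − 5⁻² = 0.960. Log OR = ln 35 − ln 24 = 0.377. SE = √(1/6.48 + 1/9.22) = 0.513. Power = Φ(0.736 − 1.96) = 11%.
- Negative binomial: SE = √[(0.600 + 0.625)/240] = 0.0714. Power = Φ(0.223/0.0714 − 1.96) = Φ(1.16) = 88%.
- Median split (more than 8): 67%.

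**Range over k = 0.3 to 1.0, 240 per arm, in %.**

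| Control mean | Controls with any event | Power, any v none | Power, median split | Power, negative binomial |
|---|---|---|---|---|
| 1 | 50.0–58.3 | 22.9–34.6 | 22.9–39.6 | 38.9–53.5 |
| 2 | 66.7–79.1 | 21.5–35.4 | 30.9–57.0 | 49.8–74.9 |
| 5 | 83.3–95.3 | 15.4–20.9 | 35.9–75.6 | 59.8–92.1 |
| 10 | 90.9–99.0 | 9.8–11.0 | 39.7–85.1 | 64.0–96.8 |
| 20 | 95.2–99.8 | 4.9–7.9 | 40.7–89.4 | 66.2–98.4 |

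At mean 20 and k = 0.3 fewer than one patient per arm is expected to have no transfusion (0.4 and 0.7), so the any-versus-none model may not be estimable and its power figure is nominal. With all 300 per arm the ordering is the same: at means 10 to 20, 5-13%, 48-95% and 74-99.6%.

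**Unequal exposure.** Assume the same readmission rate in both arms (0.2 or 0.4 per month, k = 0.5) and time on treatment of 1.25, 2.5 or 3.75 months. Let one arm have shares 25/35/40% and the other 15/35/50%. Mean time is then 2.69 and 2.94 months. Simulation gives any readmission in 36.7% v 39.3% (OR 1.11) at the lower rate and 55.5% v 58.6% (OR 1.14) at the higher, although the rate does not differ. With 240 per arm the standard error of the log OR is about 0.19 and 0.18, so the shift is roughly 0.6 to 0.7 of a standard error (0.108/0.188 and 0.128/0.185).

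**The case against.** The strongest reply is that section 8.2.1 does not say any versus none. An ordinal logistic model or a clinical threshold would fit its wording, and the analysis plan may supply either. This stands in part. A median split keeps much of the power, so the size of the loss depends on a coding that the protocol does not state. It does not remove the point, because the protocol itself fixes the model and leaves it unmatched to the outcome.

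A reader might infer that the planned method leaves almost no information, or cannot detect a real reduction in transfusions. The documents do not support that. It needs both any-versus-none coding and near-universal transfusion. The protocol calls anaemia universal, but gives no transfusion frequency.

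Readmissions are ambiguous. Sections 2.2.2 and 8.2.1 do not call them a number, and a yes/no readmission outcome suits logistic regression. Only the Trial Summary points to a count.

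A reader might also infer that complications of transplant will be compared among recipients only, which would not be a randomised comparison. No section makes that restriction. Section 8.2.1 speaks of a comparison across trial arms, so this is not part of the point.

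On exposure, any event per randomised patient is a legitimate intention-to-treat quantity, and the shift computed above is less than one standard error. An offset for time at risk also adjusts for something the intervention may change. Both objections stand, and they argue for reporting two quantities.

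**Conclusion.** The point holds in limited form. Section 8.2.1 names a binary-outcome model for transfusions, which it calls a number, and for readmissions, which the Trial Summary measures as a number. It gives no coding and no account of differing treatment length.

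The cost is conditional on assumed rates. For a 20% reduction in transfusions at a mean of 10 to 20, power falls from 64-98% with a count model to 40-89% with a median split, or to 5-11% coded any versus none. If readmissions are meant as a count with mean 1 to 2, it falls from 39-75% to 22-35% coded any versus none. All of these rest on a rate ratio of 0.8, 240 per arm and dispersion of 0.3 to 1.0, none of which the protocol gives for these outcomes. The effect of unequal exposure is real in direction but modest under the values assumed.

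These are secondary outcomes with no power claim. The primary fatigue analysis and the sample size are not affected.

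**What to change.** Reword section 8.2.1 and carry the same text into the analysis plan:

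1. Analyse the number of transfusions by negative binomial regression, adjusted for the minimisation factors in section 4.4.1. Do the same for the number of admissions if the Trial Summary's count is intended; otherwise state that the outcome is any readmission.
2. Define the window from randomisation, and reconcile the EOT limit in section 8.3 with the later questionnaires in section 4.9. State how death within the window is handled, and show deaths by arm alongside.
3. Report both the count per randomised patient and the rate with log time at risk as offset, because time on treatment may itself respond to the intervention.
4. Keep logistic regression for outcomes that are truly binary: completion of the treatment plan, any ICU admission, and any readmission if that is what is meant.

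The cost is a wording change, best made before outcome data are analysed. Section 8.3 already collects numbers of transfusions and admissions, and section 8.2.1 already foresees using the timing of transfusions. The protocol does not say that admission dates are recorded, so the case report form should be checked. No change to sample size is needed.

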### **8.2.2 Planned recruitment rate**

PROPEL aims to recruit 600 participants from approximately 50 centres across the UK over 30 months. Recruitment projections are based on a recruitment rate of 0.5 patients per month per site for the majority of the study to provide an average of 20 patients per month over the whole 30-month period. Our site surveys have demonstrated that at least 70 hospitals have expressed an interest in collaboration and estimated that around 1-2 patients per month may be eligible for recruitment. The projected rates allow for a 50% patient acceptance rate. A 12-month internal pilot phase has been incorporated into the trial to assess the willingness of clinicians and patients to participate.

### **8.2.3 Summary of baseline data and flow of patients**

Descriptive statistics will be used to summarise the distribution of the baseline variables across trial arms. Continuous baseline variables will be reported with means and 95% confidence intervals (95% CI), if normally distributed, or otherwise with medians and Interquartile Ranges (IQR). Categorical variables will be reported with frequencies and percentages.

A CONSORT [52] flow diagram will be produced.

